5.6.2. Retention of documents

Storage is maintained for 5 years at either the TKL facility at [name] in a secured room accessible only to TKL employees, or at an offsite location that provides a secure environment with burglar/fire alarm systems, camera detection, and controlled temperature and humidity. Originals or copies of the CRFs, source documents, correspondence, IRB documents, study reports, etc. will be available for the Sponsor's review on the premises of TKL or at a secure location off-site. All database management activities can be found in the data management plan (DMP).

5.7. Product handling and accountability

All product supplies are to be used only for this clinical study and not for any other purpose. Study product supplies must be kept in an appropriate, secure area (e.g., locked cabinet) and stored according to the conditions specified on the product labels.

The PI or a designee must maintain a full record of the shipment and application of study product in a product accountability ledger. This log must be kept current and should contain the following information:

- identification of the subject to whom the study product was dispensed,
- date(s) of the study product dispensed to the subject, and
- initials of the study site representative(s) dispensing study product.

The inventory must be available for inspection by the study monitor. A product-inventory and storage-facility inspection will be conducted at appropriate time intervals throughout the clinical investigation, depending on enrollment and the length of the study. Any discrepancy and/or deficiency must be accounted for by the PI or his/her designee.

The PI must not destroy any product labels, or any partly used or unused product supply. At the conclusion of the study and, as appropriate, during the course of the study, all study product supplies, including partially used or empty containers, must be returned according to the designation of the Sponsor. Any missing supplies will be indicated on the inventory; the original inventory list will be retained in the PI's records for this clinical study.

5.8. Quality control and quality assurance

5.8.1. Monitoring procedures

During the study, the Sponsor may visit the site regularly to check the completeness of subject records, the accuracy of entries on the CRFs, the adherence to the protocol and to ICH-GCP guidelines, the progress of enrollment, and also to ensure that study product is being stored, dispensed and accounted for according to specifications. Key investigative personnel will be available to assist the field monitor during these visits.

The data required by the protocol must be recorded on the appropriate CRFs. The CRFs and any source documents will be available to the study monitor who will perform a 100% data check (comparison of the data recorded in the CRF with those in the source documents). The CRFs and source data will also be available for an audit by the Sponsor or the FDA at any time.

The Investigator will give the monitor access to relevant clinical records, to confirm their consistency with the CRF entries. No information in these records about the identity of the subjects will leave the study center. Additional checks of the consistency of the source data with the CRFs are performed according to the study-specific monitoring plan.

5.8.2. Auditing procedures

In addition to the routine monitoring procedures, a study center may be audited in depth for study quality assurance by the Sponsor, an external auditor on behalf of the Sponsor, and/or by regulatory authorities. This audit may include a review of all source documents, drug records, and original CRFs the study site used in this study. Subject confidentiality will be maintained at all times and consent for this will be obtained before entry of the subject into the clinical study (see [Section 5.3](#)). If an inspection is requested by a regulatory authority, the PI must immediately inform the study Sponsor that this request has been made.

5.9. Confidentiality and publication policies

5.9.1. Disclosure and confidentiality

By signing the protocol, the PI agrees to keep all information provided by the Sponsor in strict confidence and to request similar confidentiality from his/her staff and the IRB. Study documents provided by the Sponsor (protocols, IBs, CRFs and other material) will be stored

appropriately to ensure their confidentiality. The information provided by the Sponsor to the PI may not be disclosed to others without direct written authorization from the Sponsor, except to the extent necessary to obtain informed consent from subjects who wish to participate in the study.

5.9.2. Communication and publication of results

Any formal presentation or publication of data from this study will be considered as a joint publication by the Investigator(s) and appropriate Sponsor personnel. Authorship will be determined by mutual agreement.

Sponsor must receive copies of any intended communication in advance of publication (at least 15 working days for an abstract or oral presentation and 45 working days for a journal submission). The Sponsor will review the communications for accuracy (thus avoiding potential discrepancies with submissions to health authorities), verify that confidential information is not being inadvertently divulged and provide any relevant supplementary information.

## **1. STUDY PROTOCOL AND AMENDMENTS**

This Statistical Analysis Plan is based on the Final Protocol dated 10 January 2019.

## **2. OBJECTIVES**

The primary objective of this study will be to determine the photoallergic potential of MC2-01 cream when topical application to healthy skin is followed by light exposure. In addition, safety will be assessed by evaluation of any AEs reported during the study.

## **3. STUDY DESIGN**

This will be a randomized, double-blind, single-center, controlled, within-subject comparison study of the investigational products (IPs), MC2-01 cream, MC2-01 vehicle, and an untreated irradiated control site in healthy volunteer subjects. A total of 8 application sites (2 cm x 2 cm each) will be marked on the subject's back and distributed so that 4 sites are on one side of the back for induction, and 4 sites are on the other side for challenge patches. The IPs will be applied in two sets. One set of patches on the back will be designated for irradiation after approximately 24 hours ( $\pm$  4 hours) of study product application and the other set will remain non-irradiated. An additional site will be marked on the back during Challenge. The site will receive no treatment but will be irradiated at Challenge to serve as an untreated irradiated control.

A defined area (approximately 50 cm^2) on the infrascapular region of each subject's back will be irradiated to determine the minimal erythema dose (MED) of ultraviolet (UV) light.

During the 3-week Induction Phase of the study, 0.2 g of each study product will be applied to 2 sites twice each week (Monday and Thursday) for approximately 24 hours ( $\pm$  4 hours) under semi-occlusive patch conditions (6 applications). After patch removal, all application sites will be evaluated, and one application site of each study product will be irradiated with 2 times the subject's MED using the full Xenon lamp spectrum. The sites will be evaluated by a trained evaluator. All sites will be reevaluated post irradiation, at approximately 48 hours later when irradiated on Tuesdays and at approximately 72 hours later when irradiated on Fridays except when irradiated on the last Friday of the Induction Phase or after the last make-up visit (if required), the sites will not be evaluated because these readings are not used for determination of photosensitization and any response will have subsided by Monday. These procedures will be performed each week for 3 weeks of the Induction Phase. Dermal reactions at the application sites will be evaluated using a visual scale that rates the degree of erythema, edema, and other signs of cutaneous irritation.

At the end of the Induction Phase, the subjects will enter a Rest Period of 10-17 days and then a Challenge Phase. One application/irradiation session may be missed during the Induction Phase. If a subject misses an irradiation session during the Induction Phase, an additional application/irradiation session will be scheduled the Monday of rest period (week 4).

---

*Statistical Analysis Plan*

---

At Challenge, each study product will be applied in an amount of 0.2 g to 2 naive sites once for approximately 24 hours ( $\pm 4$  hours) under semi-occlusive patches. After 24 hours ( $\pm 4$  hours) of product application, all sites will be evaluated, and one application site of each product and the additional untreated site will be irradiated. The sites will be examined for dermal reactions at approximately 24 hours ( $\pm 4$  hours), 48 hours ( $\pm 4$  hours), and 72 hours ( $\pm 4$  hours) post-irradiation. A Rechallenge should be performed if a cutaneous response observed during the Challenge Phase indicates possible photosensitization or at the discretion of the Investigator.

The safety endpoints for this study are irritation responses during the Induction Phase, positive responses at Challenge (ie, reactions indicative of a sensitization response) and AEs.

## **4. DATA SETS**

The study database will be constructed and maintained by TKL Data Management in accordance with its standard operating procedures (SOPs) and the Sponsor's specifications. A data management plan (DMP), including database/screen design specifications, CRF review guidelines, coding instructions, and edit check specifications will be submitted to the Sponsor for review prior to data entry. When the database has been declared to be complete and accurate as per the DMP, the database will be locked (i.e., the database software will not allow any further additions to, removals from, or other edits of the database). All changes to the database after that time must be authorized by the Sponsor in writing and a database unlock form and then the re-lock form will be signed by both TKL and Sponsor. Study Data Tabulation Model (SDTM) datasets will be constructed from the raw data sets. Analysis datasets (ADaM) that are necessary for table analyses will be generated from SDTM.

The study SDTM and ADaM datasets will be taken as input to validated SAS programs which generate the report-ready tables and listings. Each output display will show the names of the data sets and SAS program used to produce it. Upon completion of the study report, the data sets will be provided to the sponsor as SAS XPT transport files. Data sets will be CDISC compliant. A CDISC compliant define.xml and annotated CRF for SDTM datasets will also be provided to the sponsor.

## **5. HARDWARE AND SOFTWARE**

Statistical analysis will be performed following TKL SOP 03-02-04 Preparation of Tables and Listings for Statistical Reporting. All statistical analysis will be performed using SAS Version 9.2 or higher with program code prepared specifically for the project by qualified TKL statisticians and SAS programmers.

The SAS programs will generate rich-text-formatted (RTF) output with the "RTF" extension using the SAS Output Delivery System (ODS). The summary tables and listings will be formatted using the Courier New 9-point font. The RTF output is included in report documents prepared with Microsoft Word and converted to PDF format without typographical change.

---

*Statistical Analysis Plan*

---

## **6. CODING**

The Medical Dictionary for Regulatory Activities (MedDRA, Version 22.0 2019) coding dictionary will be used for the assignment of system organ class and preferred terms to AEs. The WHO Drug Dictionary Enhanced (WHO DDE Version B 1Q19) will be used for assignment of preferred terms and drug classifications (i.e., Anatomic-Therapeutic-Chemical [ATC] subgroups) to concomitant medications, as described in the Data Management Plan (DMP).

## **7. STATISTICAL DATA REVIEW**

Data verification activities to be performed prior to delivery of the SAS datasets to the project statistician are described in the approved DMP. After completion of the data verification activities, the SAS datasets will be delivered to the project statistician along with documentation of any unresolved queries and data conventions applied that are not fully explained in the data or the DMP. After delivery of the SAS datasets and prior to unblinding of the study data, the project statistician will perform completeness and self-consistency checks of the study data. Queries will be issued to the Data Manager and resolved before closure of the database.

## **8. HANDLING OF MISSING DATA**

Missing values will not be imputed.

## **9. DATABASE CLOSURE**

After completion of all data review procedures, validation of the project database, and approval of the final database in writing by the Sponsor, the database will be closed (“locked”). After the closure of the clinical database and authorization to unblind the study, the treatment codes will be merged to the analysis data sets. Any changes to data, coding, populations, or analysis plan after database closure must be approved by the Sponsor, in writing, and TKL management, and documented in the study archive with a detailed explanation of changes and reasons for changes.

## **10. INTERIM AND SUBGROUP ANALYSES**

No interim or subgroup analyses are planned.

## **11. STATISTICAL EVALUATION**

### **11.1 General Considerations for Data Analyses**

The focus of the statistical analysis will be the comparison with controls of the photoallergic response to the investigational product. The parameter for photoallergy will be the mean numerical

---

***Statistical Analysis Plan***

---

equivalent score. The diagnosis of a reaction indicative of photosensitivity will be made by the Principal Investigator according to working criteria described in detail in the study protocol. Photosensitivity is not to be determined by statistical methods. However, a supportive statistical analysis of numerical photoirritation scores during the Induction Phase will be performed.

All statistical processing will be performed using the SAS® system (version 9.2).

## **11.2 Subject Populations for Analysis**

Three analysis populations will be defined. All subjects who receive treatment will be evaluable for AEs (Population III). The evaluation of photosensitization will be based on all subjects who complete the challenge phase of the study (Population I). The analysis of local tolerability will be based off all subjects who complete the induction phase of the study (Population II).

### **11.2.1. Population I**

Photosensitization potential for each test product site will be assessed only among subjects completing the Induction and Challenge Phases for that product. To be considered a complete case for a particular test product, a subject must have 6 applications/irradiation and no less than 11 **subsequent** readings during Induction, 10-17 days rest, and 1 application and at 3 post-irradiation evaluations during Challenge for that product. However, those subjects who demonstrate photosensitization, even though they have not completed all visits, will also be included in this population and will be evaluated. If subject's patch sites were discontinued because they were considered by the Investigator to be pre-photosensitized during Induction, this subject will not be included in this population for that test product.

### **11.2.2. Population II**

Photoirritation potential for each test product will be assessed only among subjects completing the Induction Phase. To be considered a complete case for each test product, a subject must have 6 applications/irradiation as scheduled in the Induction Phase and no less than 11 **subsequent** readings as scheduled during the Induction Phase for that product.

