At the end of the Induction Phase, the subjects will enter a Rest Period of 10-17 days and then a Challenge Phase. One application/irradiation session may be missed during the Induction Phase. If a subject misses an irradiation session during the Induction Phase, an additional application/irradiation session will be scheduled the Monday of rest period (week 4).

At Challenge, each study product will be applied in an amount of 0.2 g to 2 naive sites once for approximately 24 hours (\pm 4 hours) under semi-occlusive patches. After 24 hours (\pm 4 hour) of product application, all sites will be evaluated, and one application site of each product and the additional untreated site will be irradiated. The sites will be examined for dermal reactions at approximately 24 hours (\pm 4 hours), 48 hours (\pm 4 hours), and 72 hours (\pm 4 hours) post-irradiation. A Rechallenge should be performed if a cutaneous response observed during the Challenge Phase indicates possible photosensitization or at the discretion of the Investigator.

The safety endpoints for this study are irritation responses during the Induction Phase, positive responses at Challenge (ie, reactions indicative of a sensitization response) and AEs.

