3.3.3. Interruption or Discontinuation of Treatment

A reaction of at least moderate erythema (2) accompanied with mild, but definite edema (1) to a study product observed after the first patch application/irradiation sequence of the Induction Phase may indicate the subject to be pre-sensitized and may cause the discontinuation of the subject from the study.

After the second reading of the Induction Phase, either of the following conditions will require that the study product be applied to a naïve patch site under open patch conditions:

- Reaction of >50% “p” or “p” with no erythema, mild but definite erythema, moderate or severe erythema; or “D” (see [Table 3](#) and [Table 4](#));
- Any reaction of definite erythema (mild, moderate or severe) with definite edema.

Study product may not be relocated more than twice.

If the reactions noted above occur on an irradiation day during the Induction Phase, the sites will not be able to be irradiated. Patches will be relocated at the subject’s next visit.

The 3 weeks of continuous patch contact during the Induction Phase frequently results in tape-related irritation that is exacerbated by warm weather, but which occurs among some individuals irrespective of the season. Tape-related irritation will not be graded as a photosensitivity response at the patch site but will be noted separately on the case report form (CRF). Severe tape-related irritation will necessitate a change in the application site. As above, the application site will only be changed twice and then the subject must be discontinued.

One application/irradiation session may be missed during the Induction Phase. In case of a missed application/irradiation, an additional application/irradiation during Week 4 must be

performed. In this case, no evaluation will be required following irradiation. Only one missed patch application or irradiation is allowed. A subject must be discontinued and considered not complete if more than one application or irradiation is missed.

In accordance with legal requirements and ICH-GCP guidelines, every subject has the right to refuse further participation in the study at any time and without providing reasons (see also [Section 5.3](#)). A subject's participation is to be terminated immediately upon his/her request. The Investigator should seek to obtain the reason and record this on the CRF.

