4.3. Subject Populations for Analysis

All subjects who receive treatment will be evaluable for AEs. The analysis of local tolerability (photoirritation) will be based off all subjects who complete the Induction Phase of the study. Subjects who completed Induction are those who have received at least 6 applications/irradiation of study products, and at least 11 subsequent evaluations during Induction. The evaluation of photosensitization will be based on all subjects who complete the Challenge Phase of the study. Subjects who completed Challenge are those who have received at least 6 applications/irradiation of study products, and at least 11 subsequent evaluations during Induction, completed the Rest Phase and have received one application of study products at Challenge, subsequent irradiation and complete the 3 post-irradiation evaluations for that product.

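### A subject discontinued before Day 19 because of a strong skin reaction has no Induction score in any planned display with a stated population

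*SAP*

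**What the plan says.** Induction irritation is a safety endpoint. Protocol 3.1, repeated in SAP 3, states: "The safety endpoints for this study are irritation responses during the Induction Phase", and then adds positive Challenge responses and AEs.

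The set for analysing it is completers. SAP 11.2.2 states: "Photoirritation potential for each test product will be assessed only among subjects completing the Induction Phase". For each product, "a subject must have 6 applications/irradiation as scheduled in the Induction Phase", together with no fewer than 11 readings. Protocol 4.3 has the same minima: "Subjects who completed Induction are those who have received at least 6 applications/irradiation of study products, and at least 11 subsequent evaluations during Induction".

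Three places promise more. SAP 11.7, SAP 11.8 and Protocol 4.6.1 all say that every assigned score will be given as frequency counts by treatment and time point. None of these sentences limits this to completers.

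Protocol 3.3.3 lets a reaction end participation or interrupt the sequence:

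- At least moderate erythema with mild edema after the first application/irradiation sequence "may indicate the subject to be pre-sensitized and may cause the discontinuation of the subject from the study".
- After the second reading, stronger reactions lead to relocation, and "Study product may not be relocated more than twice".
- The tape-irritation paragraph adds: "As above, the application site will only be changed twice and then the subject must be discontinued".
- "If the reactions noted above occur on an irradiation day during the Induction Phase, the sites will not be able to be irradiated".

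**The concern.** The rule that admits a subject to the Induction displays depends on finishing Induction, and a strong reaction is one of the reasons for not finishing. The measured outcome can therefore remove its own record. This differs from ordinary dropout, because the scores left out would tend to be the high ones.

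The usual safety net is also missing. Protocol 3.6.1, 3.6.2.1 and 3.6.6 say that a response which can be graded with Protocol Tables 3 and 4 is not an AE, so the AE displays do not pick it up. A reader of the study report could see an Induction irritation table without strong reactions and not learn, from any score, that a subject was stopped because of one.

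**Working it through.** **1. Reproduce the figure of 11.** From SAP Table 14.1.3 and Protocol Table 2:

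- Readings: Days 2, 4, 5, 8, 9, 11, 12, 15, 16, 18, 19 = 11.
- Applications: Days 1, 4, 8, 11, 15, 18 = 6.
- Irradiations: Days 2, 5, 9, 12, 16, 19 = 6.

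Protocol Table 2 (footnote d) has no reading after the last irradiation. The minimum of 11 is thus also the maximum, and there is no spare reading.

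**2. What a stopped subject can accumulate.**

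| Last day attended | Readings | Irradiations |
|---|---|---|
| 4 | 2 | 1 |
| 9 | 5 | 3 |
| 12 | 7 | 4 |
| 18 | 10 | 5 |
| 19 | 11 | 6 |

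Anyone stopped before Day 19 has at most 10 readings and 5 irradiations, and fails both criteria.

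**3. When a reaction can stop a subject.**

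- First sequence: the threshold sum is 2 + 1 = 3. The first reading after that irradiation is Day 4, which is reading 2 of 11. Discontinuation is discretionary.
- Relocation limit: with one trigger per application, counting only readings after the second, the triggers fall at the earliest on Days 5, 9 and 12. A third relocation cannot be needed before Day 12 (reading 7), or Day 9 (reading 5) if the second reading can itself be a trigger. That the subject must then leave is said only in the tape-irritation paragraph.
- Withheld irradiation: the Protocol does not say whether this counts as a missed irradiation, so this route is unsettled.

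The first route is enough for the point; the other two depend on unclear wording.

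**4. Where the Induction scores of such a subject could appear.**

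| Display (SAP 15) | Population in shell | Shows them? |
|---|---|---|
| Tables 14.2.1.1, 14.2.1.2 (Parts I and II) | II | No |
| Listing 16.2.6.1 | II | No |
| Listing 16.2.6.2 | None stated; produced if needed | Possibly, residual responses at relocated sites |
| Tables 14.2.1.3, 14.2.1.4 | I | No, Challenge scores only |
| Listing 16.2.6.3 | All randomized | No, Challenge scores only |
| AE tables and Listing 16.2.7.1 | III | No, gradable reactions are not AEs |
| Table 14.1.3; Listings 16.2.1, 16.2.2, 16.2.9 | All randomized | No score columns |

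Population I keeps non-completers who demonstrate photosensitization, but it excludes pre-photosensitized subjects for that product. Population II has no exception for non-completers.

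**5. Size, under assumptions.** The documents give no rate of reaction-driven stops. Assume k = 1, 2 or 3 subjects stopped at Day 4 beside 50 completers.

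- Share left out, k/(50 + k): 1/51 = 2.0%, 2/52 = 3.8%, 3/53 = 5.7%.
- Reading 2, if no completer scored 3 or more: the table shows 0/50 (exact 95% CI 0 to 7.1%) instead of 1/51 (0.05 to 10.4%), 2/52 (0.5 to 13.2%) or 3/53 (1.2 to 15.7%). From reading 3 on, such subjects have no scores to add.
- Mean score: shift = (50m + ks)/(50 + k) − m = k(s − m)/(50 + k), where m is the completer mean (0 to 1.0) and s the stopped subject's site mean, from 1.5 (readings 0 and 3) to 3.0 (both 3). Lowest: 1 × (1.5 − 1.0)/51 = 0.010. Highest: 3 × (3.0 − 0)/53 = 0.170. Even at the scale maximum of 5 on both readings, 3 × 5/53 = 0.28.

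**The case against.** The completer set is specified in advance and consistently in both documents. SAP 11.1 calls the Induction analysis supportive, and photosensitivity is not decided by statistics. A first-sequence reaction may point to prior sensitization rather than photoirritation, so leaving it out of the ANOVA is defensible. All of this stands, and it is a reason to keep Population II for the ANOVA. It does not explain why even the by-subject Induction listing is limited to completers when the Challenge listing covers all randomized subjects.

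The sentences on all assigned scores could be said to govern, so that only the shells are too narrow. But the completer restriction also stands in the text of SAP 11.2.2, and the outputs will be programmed from the shells. The two need to be aligned.

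The stop itself can be traced. Listing 16.2.1 gives end-of-study status, Listing 16.2.9 carries comments, the scores are on the CRF, and SDTM datasets are delivered. Nothing is lost from the database. However, these listings hold no scores, and the withdrawal reasons in Protocol 3.3.4 have no category for a patch-site reaction.

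Three stronger readings are tempting and are not supported:

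- That strong reactors as a group disappear. A subject relocated once or twice who still completes stays in Population II, with scores counted.
- That no planned output can hold any of these scores. Listing 16.2.6.2 might show some residual ones.
- That a product stopped on its own, as SAP 11.2.1 foresees, certainly vanishes. It drops out of the tables under the per-product rule. But Listing 16.2.6.1 has columns for both products, Listing 16.2.1 has one Population II column per subject, and the SAP does not say whether the stopped product's cells still print.

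**Conclusion.** The point holds for a subject discontinued before Day 19 because of a strong reaction: no planned display with a stated population shows that subject's Induction scores, contrary to the promise to summarize all of them. For a stop of one product only, it holds for the tables and is open for the listing.

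The number of such subjects is unknown and may be zero. Under the assumed 1 to 3 stops, the effect on mean scores is small; what matters is that the most informative reactions can go unseen. For the stopped product, displayed irritation can be understated.

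A reader might infer that the cream-versus-vehicle contrast is biased in favour of the cream, or that the photosensitization conclusion is at risk. The documents support neither. Discontinuing a subject removes both products' scores, so the direction of any effect on the contrast is unknown. The diagnosis is made by the Investigator from Challenge, and Rechallenge if needed. The point is worth fixing, but it does not undermine the primary objective.

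**What to change.** 1. Produce Listing 16.2.6.1 on all randomized subjects, as Listing 16.2.6.3 already is, and state the same population for Listing 16.2.6.2.
2. Keep Population II for the supportive ANOVA. Give the Induction frequency tables also on all treated subjects, with observed scores only, which fits the no-imputation rule of SAP 8. A sensitivity analysis of mean scores on that set is optional; its means would rest on unequal numbers of readings.
3. On Population III, summarize by product and irradiation status the subjects whose participation or sites were stopped because of a reaction, including suspected prior sensitization, with the maximum score.

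Cost: no new data. One listing gets a wider population, another gets a stated one, the frequency tables are repeated, and one summary table is added. SAP 12, which now declares no changes, needs an entry, and Protocol 4.1 asks that changes be described and justified in the final report. After database closure, SAP 9 also requires written Sponsor approval and approval by TKL management. Denominators will vary by reading, and the irritation figures may look slightly less favourable.

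Separately, Protocol 3.3.3 and 4.3 and SAP 11.2.1 and 11.2.2 should be reconciled on whether a withheld irradiation counts as missed, whether a Week 4 make-up session counts toward the 6, and whether the subject or only one product's sites are discontinued. This is a request for consistency; no stopping or relocation rule is proposed.
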